13.4.1.3. MCGI-R and MCGI-S

MCGI-R and MCGI-S will be summarized descriptively and analyzed by a CMH test stratified by total opioid dose (<90 MED, \geq 90 MED) in ITT population.

The frequency distribution across response scores will also be summarized.

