9.3. Adjustment Criteria for Opioid Taper

Subjects will be tapered from their baseline total daily dose of opioid (calculated as MED) over a 14-day period. The opioid dose will be decreased as close as possible to achieve the following dose reduction targets: 50% from the baseline MED beginning with the last dose of the day on Day -1, an additional 25% of the baseline MED beginning with the first dose of the day on Day 6, and a final 25% of the baseline MED (to dose of zero) beginning with the first dose of the day on the day on Day 13 (Figure 1). Reminders for opioid dose reduction may be done via phone, text, or other electronic message.

Opioid dosing to achieve the required dose reductions in accordance with the protocol defined taper must be planned during Screening. Any changes in opioid prescription to facilitate the protocol taper should be discussed with the subject's primary pain physician, when applicable, and prescribed in advance of randomization. The Investigator should work with a preferred pharmacy informed about the subject's participation in a clinical trial in order to fulfill prescribing needs to facilitate the opioid taper. Opioid prescriptions should be written to accommodate the planned taper, based on the following considerations:

- Subjects should be maintained on the same opioid molecule throughout the taper and not converted to new molecules.
- Priority should be given to eliminating opioid medications for breakthrough pain as part of the first opioid dose reduction (50% of baseline MED) if possible. If not possible, dosing of opioid medications being taken for breakthrough pain should be

changed to be part of a fixed dose regimen appropriate to achieve the target MED reduction.

• Opioid dose reductions should be as close as possible to the nominal reductions specified per protocol (ie, 50% or 25% reduction). Round up on the dose of the available opioid formulation if unable to adjust exactly to meet nominal MED reduction criteria.

The subject's baseline opioid regimen and MED calculation as well as the opioid regimen planned to achieve each taper step should be submitted to and approved by the Medical Monitor prior to Day -1. The Investigator will discuss and confirm the subject's agreement to comply with the opioid dosing regimen for each opioid taper step based on the Medical Monitor-approved plan.

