11.2. Clinical Opiate Withdrawal Scale (COWS)

The COWS will be used to assess effectiveness of LUCEMYRA in alleviation of opioid withdrawal [Wesson 2003]. The COWS is a clinician-administered instrument that rates 11 common opioid withdrawal signs and symptoms. These include: resting pulse rate; sweating; restlessness; pupil size; bone or joint aches; runny nose or tearing; gastrointestinal upset; tremor; yawning; anxiety or irritability; and gooseflesh skin. Lower total scores indicate a more positive clinical outcome.

The COWS completed at the Day 1 Visit (Visit 1) should be completed prior to the first dose of study drug.

A copy of the COWS assessment tool is provided in Section 16.4.

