11.3. Short Opiate Withdrawal Scale of Gossop (SOWS-Gossop)

The SOWS-Gossop scale assesses subjective symptoms of opioid withdrawal [Vernon 2016, Gossop 1990]. It is a subject-rated scale consisting of 10 items that are scored on a 4-point scale of 0 = none, 1 = mild, 2 = moderate, and 3 = severe (minimum score of 0, maximum score of 30) (Table 9). The overall score is the simple sum of the 10 item scores. Lower observed values in

SOWS-Gossop scores indicate a more positive clinical outcome. The SOWS-Gossop will be completed daily beginning at Day 1 at home at bedtime and at clinic visits (and Early Termination, if applicable). The SOWS-Gossop completed at the Day 1 Visit (Visit 1) should be completed prior to the first dose of study drug.

	Score			
Condition	None	Mild	Moderate	Severe
Feeling sick	0	1	2	3
Stomach cramps	0	1	2	3
Muscle spasms/twitching	0	1	2	3
Feeling of coldness	0	1	2	3
Heart pounding	0	1	2	3
Muscular tension	0	1	2	3
Aches and pains	0	1	2	3
Yawning	0	1	2	3
Runny eyes	0	1	2	3
Insomnia/problem sleeping	0	1	2	3

Table 9:SOWS-Gossop Scoring Method

SOWS-Gossop = Short Opiate Withdrawal Scale of Gossop

Note: possible score range is 0 to 30.

A copy of the SOWS-Gossop is provided in Section 16.5.

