11.4. Subjective Opiate Withdrawal Scale of Handelsman (SOWS-H)

The SOWS-H scale assesses subjective symptoms of opioid withdrawal [Handelsman 1987]. It is a subject-rated scale consisting of 19 items that are scored on a 5-point scale of 0 = not at all, 1 = a little, 2 = moderately, 3 = quite a bit, and 4 = extremely. The overall score is the simple sum of the 19 item scores. Lower observed values in SOWS-H scores indicate a more positive clinical outcome. The SOWS-H will be completed daily beginning at Day 1 at home at bedtime and at clinic visits (and Early Termination, if applicable). The SOWS-H completed at the Day 1 Visit (Visit 1) should be completed prior to the first dose of study drug.

Item 16 of the SOWS-H was rephrased to be more appropriate for this population [FDA 2014].

A copy of the SOWS-H is provided in Section 16.6.

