11.7. Modified Clinical Global Impression – Subject Version (MCGI-S)

The MCGI-S includes 2 items:

- A 7-point scale that allows subjects to rate the severity of opiate withdrawal symptoms.
- A 4-point scale that allows subjects to rate the degree of side effects from their study drug.

The MCGI-S will be completed once daily beginning at Day 1 at home at bedtime and at clinic visits (and Early Termination, if applicable).

A copy of the MCGI-S is provided in Section 16.9.

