13.4.1.2. COWS, SOWS-Gossop, and SOWS-H

The treatment group difference for change in COWS, SOWS-Gossop, and SOWS-H total scores from Baseline to peak value and to each scheduled evaluation will be summarized descriptively with 95% confidence intervals. The treatment group differences will be calculated within the framework of analysis of covariance (ANCOVA) with treatment and total opioid dose (<90 MED, \geq 90 MED) as fixed factors and baseline score as a covariate.

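### The MCGI withdrawal-severity items are tested without adjustment for starting withdrawal severity, although pre-dose COWS and SOWS scores are scheduled; the test is valid but may give up precision

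*Combined protocol and SAP*

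**What the plan says.** - **MCGI analysis (Section 13.4.1.3).** "MCGI-R and MCGI-S will be summarized descriptively and analyzed by a CMH test stratified by total opioid dose", with strata below 90 MED and 90 MED or above. No severity covariate is named, and neither a treatment-difference estimate nor a confidence interval is planned.
- **MCGI timing.** Section 11.7: "The MCGI-S will be completed once daily beginning at Day 1 at home at bedtime and at clinic visits". Table 2 marks clinic MCGI-S and MCGI-R from Visit 2 (Day 3). Study drug starts in clinic on Day 1 (Section 9.2.3), so even the first bedtime MCGI-S is post-dose.
- **Pre-dose withdrawal scores.** Section 11.2: "The COWS completed at the Day 1 Visit (Visit 1) should be completed prior to the first dose of study drug". Section 11.3: "The SOWS-Gossop completed at the Day 1 Visit (Visit 1) should be completed prior to the first dose of study drug". Section 11.4: "The SOWS-H completed at the Day 1 Visit (Visit 1) should be completed prior to the first dose of study drug".
- **Analysis of those scales (Section 13.4.1.2).** ANCOVA with treatment and dose stratum "as fixed factors and baseline score as a covariate". Sections 13.4.1.5 (NRS) and 13.4.1.6 (ISI, HADS, EQ-5D-5L, SF-36) also use baseline as a covariate.
- **State of the taper at the pre-dose score (Section 9.3).** The first opioid cut is "50% from the baseline MED beginning with the last dose of the day on Day -1".

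**The concern.** Each MCGI instrument has a 7-point item on the severity of opioid withdrawal. That is what COWS rates from the clinician's side and SOWS from the subject's. Subjects who start with more withdrawal may well score higher later. If so, the unadjusted comparison carries between-subject variation that a scheduled covariate could remove, and a chance Day 1 imbalance between arms stays in the estimated contrast. Stratifying by dose helps only as far as dose predicts severity.

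The plan adjusts its other scored scales for baseline and gives no reason for the exception. The likely reason is that MCGI has no baseline of its own, but a proxy is available. At stake is precision on two secondary endpoints of a 60-subject pilot meant to inform a pivotal study.

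**Working it through.** **Inputs from the protocol.** 60 subjects, 1:1, 30 per arm (Section 7.3); two dose strata (Section 9.1.1); 7-point severity items (Sections 11.7 and 11.8).

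**Inputs not given, so assumed.** Rho from 0 to 0.7; standardised effect d of 0.6 or 0.74; two-sided 5% test.

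**1. The plan's own figure.** Section 13.2 gives 95% CI half-widths of 0.24 (20 per group) and 0.17 (40 per group) for a difference in proportions of 0.2. With assumed rates of 0.10 and 0.30 and no continuity correction, 1.96 × √[(0.10×0.90 + 0.30×0.70)/n] gives 0.240 at n = 20 and 0.170 at n = 40. At the planned n = 30 it gives 0.196. These figures concern withdrawal-event incidence; nothing in the sample-size section bears on MCGI.

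**2. Continuous approximation.** Adjustment multiplies the residual variance by 1 − rho². Power = Φ(d√(n/2)/√(1 − rho²) − 1.96). With d = 0.6 and n = 30, d√(n/2) = 0.6 × √15 = 2.324.
- rho 0: Φ(0.364) = 64%
- rho 0.3: Φ(2.324/0.954 − 1.96) = 68%
- rho 0.5: Φ(2.324/0.866 − 1.96) = 77%
- rho 0.7: Φ(2.324/0.714 − 1.96) = 90%

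This treats MCGI as continuous and normal, so it is only a guide.

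**3. Ordinal simulation, closer to the planned test.** Seven categories cut from a latent normal score at cumulative probabilities 0.25, 0.50, 0.70, 0.85, 0.94 and 0.98; two equal strata; 30 per arm; a skewed integer baseline; rho on the latent scale; 6,000 runs per cell. The rank (mean-score) CMH test is compared with stratified rank ANCOVA, which is the same statistic on residuals after regressing ranks on baseline ranks.

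| rho | CMH, d = 0.6 | Rank ANCOVA, d = 0.6 | Change (points) | CMH, d = 0.74 | Rank ANCOVA, d = 0.74 | Change (points) |
|---|---|---|---|---|---|---|
| 0 | 55.5% | 54.2% | −1.3 | 73.2% | 71.7% | −1.5 |
| 0.2 | 56.2% | 56.0% | −0.2 | 72.1% | 72.3% | +0.2 |
| 0.3 | 55.5% | 56.5% | +1.0 | 72.4% | 73.5% | +1.1 |
| 0.5 | 55.9% | 62.8% | +6.9 | 73.8% | 81.3% | +7.5 |
| 0.7 | 57.2% | 76.6% | +19.4 | 74.3% | 90.5% | +16.2 |

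A second simulation of this kind gave about −2 points at rho 0, +2 at 0.3, +9 at 0.5 and +22 at 0.7. Type I error was about 4.4% to 5.4% throughout, for both methods.

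**4. Chance imbalance.** The standard error of the standardised Day 1 difference between arms is √(2/30) = 0.26 SD. At rho 0.5, a one-standard-error imbalance moves the unadjusted contrast by 0.5 × 0.26 = 0.13 SD, or 0.13/0.6 = about a fifth of a 0.6 SD effect.

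**5. A condition on the starting power.** Section 13.4.1.3 does not say which CMH statistic is meant. In the first simulation at d = 0.6, the general-association version had about 24% power, against about 56% for the mean-score version used above.

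**The case against.** A CMH test stratified by the randomisation factor is a valid, conventional choice for an ordinal scale with no baseline of its own. Its type I error already covers chance imbalance, so imbalance is not bias. **This stands in full.**

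A reader might infer that power is certainly being thrown away, perhaps from the continuous formula's rise from 64% to 77% at rho 0.5. **The documents do not support that.** They give no correlation, MCGI effect size or power target. The corresponding ordinal gain is about 7 to 9 points.

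A high rho is also open to doubt. Day 1 scores come just after the first cut begins, no minimum withdrawal score is needed for entry, and later ratings follow further cuts and investigator-guided dosing. Scores may be low and compressed. COWS and SOWS are different instruments from MCGI, so this is proxy adjustment.

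The secondary objective is to estimate differences (Section 6.2). Precision is therefore the better yardstick, and a rank-ANCOVA p-value alone does not serve that objective. COWS and SOWS already receive baseline-adjusted analyses, so no conclusion on withdrawal rests on MCGI alone. Section 13.1 leaves details to a later SAP, which may yet add this.

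These points limit the size and priority of the concern. They do not remove it: the covariate is scheduled and measured before study drug, and adjusting for it is valid.

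**Conclusion.** The point holds as a modest improvement. The MCGI severity items are tested with no term for starting withdrawal severity, although a pre-dose measure of the same construct is scheduled for every subject and baseline is used for the other scored scales.

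At an assumed 0.6 SD effect, the benefit is negligible for rho up to 0.3, worth having at 0.5 and substantial at 0.7. If the covariate is not prognostic, the cost is 1 to 2 points of power. These figures rest on the assumed effect, category probabilities, equal strata and baseline shape, and on a mean-score CMH as comparator.

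Two stronger inferences are not supported: that the planned test is wrong, and that a known amount of power is lost. Nor can it be said that every subject will have a pre-dose score; the protocol schedules one but does not guarantee it.

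**What to change.** In the SAP, before the unblinded interim at about 30 subjects (Section 13.5), prespecify for the 7-point severity items only:

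- **MCGI-R:** an analysis stratified by MED and adjusted for pre-dose Day 1 COWS.
- **MCGI-S:** the same, adjusted for pre-dose Day 1 SOWS-Gossop.
- **Method:** stratified rank ANCOVA, or a proportional-odds model with treatment, dose stratum and the covariate. The latter also gives a treatment-difference estimate with a 95% CI and so fits the objective better. Its odds ratio is conditional on baseline severity and should be labelled so.
- **Support:** keep the unadjusted CMH test and name the statistic used.
- **Missing pre-dose scores:** fill with the stratum mean, pooled over arms.

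The 4-point side-effect items stay as planned, since withdrawal severity is not a natural baseline for them.

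The cost is a short SAP addition and minor programming, with no new data collection. The downsides are the fill-in rule and the small loss if the covariate proves uninformative. Reporting the observed correlation would also help in planning the pivotal study.

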13.4.1.4. Time to Study Drug Discontinuation

Time to study drug discontinuation will be summarized descriptively with a Kaplan-Meier curve stratified by total opioid dose (<90 MED, $\geq 90 \text{ MED}$) in ITT population. In addition, the treatment group difference will be assessed with the log-rank test.

13.4.1.5. Numerical Rating Scale

Treatment group differences for each NRS score will be assessed as follows:

- Average of daily values from Day 1 through EOS Visit
- Change from Baseline (average of Days -3 to -1) to the average of the last 3 days before the EOS Visit
- Graphical display of daily means

Treatment differences for average of daily values and for change from baseline will be assessed with an ANCOVA with treatment and total opioid dose (<90 MED, $\geq 90 \text{ MED}$) as fixed factors and Baseline value (average of Days -3 to -1) as covariate. In addition, 95% confidence intervals for the treatment group differences will be calculated within the framework of the ANCOVA.

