8.6. Early Discontinuation Visit

If a subject is discontinued from the study before completion, regardless of whether they have received study drug, the reason for discontinuation must be documented in the subject's source document and eCRF. Whenever a subject is discontinued, the procedures/assessments listed for the EOS Visit in the Schedule of Assessments (Table 2 or Table 3) should be performed. If a subject discontinues on a scheduled visit, assessments completed at that visit should be entered into the eCRF for that scheduled visit. Assessments required for the EOS Visit that are not required at the scheduled visit (eg, a complete physical examination, clinical laboratory tests) should be completed and entered into the eCRF for the EOS Visit.

Subjects who prematurely discontinue the study will be instructed to taper study drug as described in Section 9.2.3 and to complete the at-home assessments for the study drug taper period (Table 4 or Table 5). Once discontinued, subjects may not re-enter the study.

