11. ASSESSMENTS OF EFFECTIVENESS

11.1. Numeric Rating Scale (NRS) of Pain Intensity

The NRS of pain intensity is a unidimensional, segmented numeric version of the visual analog scale. A subject selects a whole number (0 to 10) that best indicates the intensity of his/her pain. The format consists of a horizontal line which is anchored by terms defining pain levels where 0 represents no pain and 10 represents worst pain imaginable.

At bedtime, subjects will answer the following questions regarding daily pain intensity:

How would you rate the average pain due to your current chronic pain condition over the last 24 hours?

How would you rate the worst pain due to your current chronic pain condition over the last 24 hours?

Sometimes when people come off opioids, they feel aches and pains all over their body. How would you rate the average pain, all over your body over the last 24 hours?

Sometimes when people come off opioids, they feel aches and pains all over their body. How would you rate the worst pain, all over your body over the last 24 hours?

NRS chronic pain scales will be completed daily at home before bedtime beginning at Screening through the 30-day follow-up phone call and at clinic visits (and Early Termination, if applicable). NRS all over body pain scales will be completed at home before bedtime beginning on Day 1 through the EOS Visit and at clinic visits (and Early Termination, if applicable). NRS scales completed at the Day 1 Visit (Visit 1) should be completed prior to the first dose of study drug.

A copy of the NRS is provided in Section 16.1.

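### Four of the eight planned NRS ANCOVAs lack the stated baseline; separately, the end-of-study pain change pools completers' off-drug days with early discontinuers' possibly on-drug days

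*Combined protocol and SAP*

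**What the plan says.** Section 13.4.1.5 begins "Treatment group differences for each NRS score will be assessed as follows" and lists three items: the mean of daily values from Day 1 to EOS, a change score, and a plot of daily means. The change score is "Change from Baseline (average of Days -3 to -1) to the average of the last 3 days before the EOS Visit". The mean and the change score each go into an ANCOVA with treatment and opioid-dose stratum as factors and "Baseline value (average of Days -3 to -1) as covariate".

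Section 11.1 defines four scores: average and worst pain from the chronic condition, and average and worst pain all over the body. The chronic-pain pair is rated daily from Screening. For the other pair, "NRS all over body pain scales will be completed at home before bedtime beginning on Day 1 through the EOS Visit". The section adds that "NRS scales completed at the Day 1 Visit (Visit 1) should be completed prior to the first dose of study drug".

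For subjects who leave early, section 8.6 calls for the end-of-study procedures at that point: "Whenever a subject is discontinued, the procedures/assessments listed for the EOS Visit". These subjects are also told to taper study drug and to "complete the at-home assessments for the study drug taper period". Section 13.4.1.4 compares time to study-drug discontinuation between arms: "the treatment group difference will be assessed with the log-rank test".

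Section 7.2.2 lists change to peak in average and worst daily pain as an NRS endpoint. Section 13.4.1.5 does not mention a peak.

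**The concern.** There are three separate gaps.

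- **Baseline.** The stated baseline rule covers all NRS scores, but two of the four have no ratings on the days it names. These two ask about aches that come with stopping opioids, so they are the pain items closest to withdrawal.
- **Window.** The end window is tied to the EOS Visit, not to dosing. EOS comes about a week after the last dose for completers, but at the moment of discontinuation for those who leave early. The same variable then describes post-treatment pain in some subjects and on-treatment pain in others. If the arms differ in early discontinuation, the contrast can move with no drug effect on pain.
- **Peak.** An endpoint is listed without a window or a method.

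Timing also matters. Section 13.1 lets the analysis plan be finalised as late as just before database lock. Section 9.1.2 breaks the blind for statistical programmers and Sponsor-designated reviewers at about 30 subjects. A baseline or window chosen after that could be informed by unblinded data.

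**Working it through.** **Step 1. Reproduce the plan's treatment length.** Inputs: the opioid dose is zero from Day 13, or Day 19 with a pause (9.3; Table 3 footnotes), so the last opioid day is 12 or 18. Study drug continues 5 more days and is then tapered over 4 (9.2.3).

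- Standard: 12 + 5 + 4 = Day 21 as last dose.
- Pause: 18 + 5 + 4 = Day 27 as last dose.

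This matches the 21 to 27 days in section 7.4, and taper starts of Day 18 and Day 24 in the footnotes to Tables 2 and 3. EOS is Day 28 or 34. The gap is 28 − 21 = 7 or 34 − 27 = 7 days, as section 7.1 says.

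**Step 2. Count the models and check the baseline.** 4 scores × 2 summaries = 8 ANCOVAs.

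| Scores | First rating | Days -3 to -1 values | ANCOVAs |
|---|---|---|---|
| Chronic pain, average and worst | Screening | yes | 2 × 2 = 4 |
| All over body, average and worst | Day 1 | none | 2 × 2 = 4 |

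Tables 2 to 5 show no all-over-body rating before Day 1. For those two scores the change cannot be formed, and the covariate is missing from both models. The Day 1-to-EOS mean itself can be computed.

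**Step 3. Place the end window for completers.** The window is EOS − 3 to EOS − 1. The last dose is Day 21.

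| EOS day | Window | Days after last dose | On-drug days |
|---|---|---|---|
| 27 | 24–26 | 3–5 | 0 of 3 |
| 28 | 25–27 | 4–6 | 0 of 3 |
| 29 | 26–28 | 5–7 | 0 of 3 |

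With a pause, every day moves by 6 and the offsets are the same.

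**Step 4. Place it for early discontinuers.** If EOS procedures are done on Day 8 while the subject is still dosing, the window is Days 5–7. On Day 15 it is Days 12–14. Both have 3 of 3 days on drug.

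**Step 5. What pooling does.** Take the simplest case: no drug effect on pain, and discontinuers otherwise like completers. Then

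shift in the contrast = (difference between arms in the share with an on-drug window) × (mean pain in on-drug windows − mean pain in post-treatment windows).

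The shift is zero if the shares are equal. The documents give neither factor, so I put no number on it.

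**Step 6. The other tested summary.** On-drug share of the Day 1-to-EOS mean for completers: 21/28 = 75%, or 27/34 = 79% with a pause.

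**Step 7. Peak.** Section 7.2.2 names the endpoint. Section 13.4.1.5 has no matching analysis, and no section sets the period in which the peak is sought. Chronic-pain ratings run to the 30-day call (11.1), so the period is genuinely open.

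**The case against.** The best defence has four parts.

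- **Post-treatment pain is a legitimate question.** This stands. A reader might infer that the window misses the secondary objective because that objective concerns the taper. The documents do not support this: the pain item in section 6.2 carries no such limit.
- **On-treatment pain is already tested.** This stands for the chronic-pain scores, where the average is three-quarters on-drug days and daily means are plotted. A reader might infer from the missing baselines that no pain contrast reflects treatment. That does not follow. The baseline gap and the window are independent defects, and dilution is not loss.
- **Section 13 is only an overview.** Section 13.1 leaves details to the analysis plan. That plan can settle the peak definition, but 13.4.1.5 already states a baseline rule, and for half the models it cannot be applied. If only the chronic-pain scores were meant, there would be 4 models and none would lack a baseline. The opening words of 13.4.1.5 do not read that way.
- **The extent of mixing is unknown.** This stands. Some discontinuers may have stopped dosing before their EOS procedures, and 12.1.7.1 provides for stopping study drug with follow-up through EOS. Subjects who withdraw consent may refuse the procedures (8.5). The planned log-rank test concerns study-drug discontinuation, which is not the same event as leaving the study.

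**Conclusion.** The point holds in three limited parts.

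1. As written, 4 of the 8 NRS ANCOVAs, all for the all-over-body scores, cannot be run. This rests on reading 13.4.1.5 as covering all four scores in 11.1.
2. The end-window change has 0 of 3 on-drug days for completers on schedule and up to 3 of 3 for subjects discontinued while dosing, pooled in one model. The direction and size of any shift cannot be derived from the documents.
3. The peak-pain endpoint has no analysis or window.

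A reader might also conclude that HADS, EQ-5D-5L and SF-36 must be collected during treatment. The documents do not compel that; it is an optional trade-off that needs an amendment. It is enough to note that HADS has a one-week recall (11.5) and its only scheduled post-baseline value is at EOS. For completers that week holds 0 to 2 on-drug days over the visit window (Days 20–26, 21–27 or 22–28 against a last dose on Day 21), so the result is essentially post-treatment. The peak analysis of HADS and SF-36 in 13.4.1.6 duplicates their EOS analysis.

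**What to change.** Set the following in 13.4.1.5 or the analysis plan before the interim unblinding:

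1. For the all-over-body scores, use the pre-dose Day 1 clinic rating as baseline and covariate, and count the Day 1 bedtime rating as post-baseline. State that this baseline precedes study drug but follows the first opioid reduction, which begins with the last dose on Day -1. It is therefore valid for comparing arms, but it is not a pre-taper value and does not match the chronic-pain baseline.
2. Add an on-treatment average, Day 1 to last dose, for all four scores, using the planned ANCOVA.
3. Keep the last-3-days-before-EOS analysis, label it post-treatment, and report early discontinuers separately in it.
4. If a window of the last 3 days before study-drug taper or stop is added for the chronic-pain scores (Days 15–17 for completers, or 21–23 with a pause), report early discontinuers separately there too. Completers are then at zero opioid, whereas early discontinuers may be at another opioid step, so pooling would bring back a mixture.
5. Reconcile 7.2.2 with 13.4.1.5 on change to peak: add an analysis with a stated window, or remove the endpoint.

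Items 1 to 4 use ratings already collected, and item 5 needs only wording. The cost is a few more secondary summaries. No visit, dose or questionnaire changes.
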